9.3. Unexpected Adverse Drug Experience

An unexpected adverse experience is any adverse drug experience, the specificity or severity of which is not consistent with the current Investigator's Brochure, or if an Investigator's Brochure is not required or available, which is not consistent with the risk information described in the general investigational plan or elsewhere in the current application, as amended. "Unexpected," as used in this definition refers to an adverse drug experience that has not previously been observed (e.g., included in the Investigator's Brochure) rather than from the perspective of such an experience not being anticipated from the pharmacological properties of the pharmaceutical product.

9.4. Causality

Association of adverse events to the study drug will be made using the following definitions:

Not related: The event is most likely produced by other factors such as the subject's clinical condition, intercurrent illness, or concomitant drugs, and does not follow a known response pattern to the study drug, or the temporal relationship of the event to study drug administration makes a causal relationship unlikely

Possibly-related: The event follows a reasonable temporal sequence from the time of drug administration, and/or follows a known response pattern to the study drug, but could have been produced by other factors such as the subject's clinical condition, intercurrent illness, or concomitant drugs

Probably-related: The event follows a reasonable temporal sequence from the time of drug administration, and/or follows a known response pattern to the study drug, and cannot be reasonably explained by other factors such as the subject's clinical condition, intercurrent illness, or concomitant drugs.

9.5. Serious Adverse Event

A **serious adverse event (SAE)** is any untoward medical occurrence, that at any dose, regardless of causality:

- results in death.
- is life-threatening. Life threatening means that the subject was at immediate risk of death from the reaction as it occurred, i.e., it does not include a reaction that, had it occurred in a more severe form might have caused death.
- requires in-patient hospitalization or prolongation of existing hospitalization. Hospitalization admissions and/or surgical operations scheduled to occur during the study period, but planned prior to study

entry are not considered AEs if the illness or disease existed before the subject was enrolled in the trial, provided that it did not deteriorate in an unexpected manner during the trial (e.g., surgery performed earlier than planned).

- results in persistent or significant disability/incapacity. Disability is defined as a substantial disruption of a persons' ability to conduct normal life functions.
- is a congenital anomaly/birth defect.
- an important medical event that may not result in death, be life-threatening, or require hospitalization but may be considered a SAE when, based upon appropriate medical judgment, it may jeopardize the subject and may require medical or surgical intervention to prevent one of the outcomes listed in the definition of SAE. Examples of such medical events include allergic bronchospasm requiring intensive treatment in an emergency room or at home, blood dyscrasias or convulsions that do not result in in-patient hospitalization, or the development of drug dependency or drug abuse.

9.6. Procedures for Recording and Reporting AEs and SAEs

Adverse events, both serious and non-serious, will be reported between Day 1 (Enrollment) and the final visit (up to Weeks 26 or 39, Visits 3 or 4).

All adverse events spontaneously reported by the subject and/or in response to an open question from study personnel or revealed by observation, physical examination or other diagnostic procedures will be recorded on the appropriate page of the eCRF. Any clinically relevant deterioration in laboratory tests or other clinical finding is considered an adverse event and must be recorded on the appropriate pages of the eCRF. When possible, signs and symptoms indicating a common underlying pathology should be noted as one comprehensive event or diagnosis.

All serious adverse events occurring during the course of the study must be reported by email, or fax immediately to:

In no event shall a SAE be reported more than twenty-four (24) hours after the Investigator becomes aware of such event. The report of an SAE by the Investigator must provide the following minimal information: protocol number, subject number, subject's initials and date of birth, nature of the adverse event and attributes such as the severity of the event and causality. Events will be considered suspected adverse drug reactions if classified by the Investigator as possibly-related or probably-related.

A report of a SAE by telephone must always be confirmed by a written, more detailed

report within 24 hours of the Investigator becoming aware of the event. The SAE Reporting Forms are provided to each clinical study site in the Study Manual. The Investigator should provide the following documentation at the time of notification, if available:

- SAE Reporting Form
- Concomitant and support medication pages;
- Relevant diagnostic reports;
- Relevant laboratory reports;
- Admission notes; if applicable
- Hospital discharge summary; if applicable

Ardelyx will assume responsibility for appropriate reporting of adverse events to regulatory authorities. Ardelyx will report Suspected Unexpected Serious Adverse Reactions (SUSARs) to all investigational sites.

It is the responsibility of the Investigator to promptly notify the Institutional Review Board (IRB)/Independent Ethics Committee (IEC) of all SAEs, as well as any unanticipated problems that involve significant risk to subjects. A copy of the IRB/IEC notification should be placed in the sites' regulatory binder.

9.7. Monitoring of Adverse Events and Period of Observation

Adverse events, both serious and non-serious, will be recorded on the eCRFs up to and including the final visit (either Visit 3 (TEN-01-302) or Visit 4 (TEN-01-301)). All adverse events should be monitored until they are resolved or are clearly determined to be due to a subject's stable or chronic condition or concurrent illness(es).

Follow-up data concerning the SAE (e.g., diagnostic test reports, physician's summaries, etc.) must also be submitted to the Sponsor as they become available, preferably by facsimile. All serious adverse events, as well as any unanticipated problems that involve significant risk to subjects, must be promptly reported by the Investigator to his/her Institutional Review Board (IRB). Should the FDA or other pertinent regulatory authorities require that Ardelyx submit additional data on the event, the Investigator will be asked to provide those data to Ardelyx in a timely fashion.

The Investigator will review each serious adverse event report and further evaluate the relationship of the adverse event to the study drug and to the subject's underlying disease. Based on the Investigator assessment of the adverse event, a decision will be made concerning the need for further action. The primary consideration governing further action is whether new findings affect the safety of other subjects participating in the clinical study. If the discovery of a serious and unexpected adverse event related to the study drug raises concern over the safety of its continued administration to subjects, the Sponsor will take immediate steps to notify the FDA and other pertinent regulatory authorities and all Investigators participating in clinical studies of the study drug.

Any serious adverse event that occurs at any time after completion of the study, which the Investigator considers to be related to study drug, must be reported to Ardelyx within forty-eight (48) hours of the Investigator becoming aware of the event.

9.8. Pregnancy

Pregnancy by definition is not considered to be a serious adverse event unless the pregnancy or the outcome meets the criteria in Section 9.5. However, pregnancy in subjects that have received the study drug must be followed to assess congenital anomalies.

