8.2.1.1 Adverse events

Monitoring of treatment emergent adverse events will be conducted throughout the study beginning on Day 1. Adverse events, including serious adverse events will be recorded in the eCRFs through the end of the study. All adverse events should be followed by the investigator until they are resolved or are clearly determined to be due to a subject's stable or chronic condition or concurrent illness(es). Definitions, documentation, and reporting of adverse events are described in detail in Section 9.

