10.7.1 Subject Disposition

Subject disposition information will be summarized by treatment cohort and all subjects overall. The number and percent of subjects who are enrolled, who took a dose of study drug, who complete the study, and who withdraw early from the study will be presented. The primary reason for early withdrawal will also be tabulated. The number of subjects enrolled will be used as the denominator for the percentage calculation. Subject disposition, inclusion / exclusion criteria, and protocol deviations will be listed.

The number and percent of subjects in the safety analysis set will also be tabulated.

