11.6. Study Monitoring and On-site Audits

Monitoring and auditing procedures developed by Ardelyx or its CRO designee will be followed, in order to comply with GCP guidelines. Routine monitoring visits will be made to assure compliance with the study protocol, to review and compare the subject’s eCRF with source documents, to ensure adequate records of clinical supplies are maintained and to assess the continued suitability of the investigational site. The Investigator agrees to allow the site monitors, and other authorized personnel or designees, access to the subject’s medical records, regulatory binder, study binder, and source documents as needed to assure the conduct of the study was within compliance.

Upon completion of the study the site monitor will make a final assessment of the

conduct of the study and inventory all clinical supplies to be returned to Ardelyx. All unused study drug is to be returned to Ardelyx or designee.

Regulatory authorities, the IEC/IRB, and/or Ardelyx's clinical quality assurance group, its CRO designee or business partners may request access to all source documents, CRFs, and other study documentation for on-site audit or inspection. Direct access to these documents must be guaranteed by the Investigator, who must provide support at all times for these activities.

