11.8. Drug Accountability/Retention

Accountability for the study drug at the trial site is the responsibility of the Investigator. The Investigator will ensure that the study drug is used only in accordance with this protocol. Where allowed, the Investigator may choose to assign some of the drug accountability responsibilities to a pharmacist or other appropriate individual. Drug accountability records indicating the study drug's delivery date to the site, inventory at the site, use by each subject, and return to Ardelyx (or disposal of the drug, if approved by Ardelyx) will be maintained by the clinical site. These records will adequately document that the subjects were provided the doses as specified in the protocol and should reconcile all study drug received from Ardelyx. Accountability records will include dates, quantities, batch/serial numbers, expiration dates (if applicable), and subject numbers. Ardelyx or its CRO designee will review drug accountability at the site on an ongoing basis during on-site monitoring visits.

The Investigator acknowledges that the study drug supplies are investigational and as such must be handled strictly in accordance with the protocol and container label. Supplies should be dispensed under the supervision of the Investigator or designee. Study drug will be stored in a limited access area and under the appropriate conditions as specified on delivery.

Unused or partially used bottles of study drug will be stored until the study monitor at

the end of the study performs a final inventory. At the completion of this trial, all unused, partially unused, or empty multiple-dose bottles must be returned to Ardelyx, or designee.

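### Pregnancies exposed to study drug must be followed for anomalies, but sponsor notice is not required, late anomalies judged unrelated may go unreported, and no rule stops dosing

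*Protocol*

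**What the plan says.** **Follow-up.** Protocol 9.8 has two sentences. The first keeps pregnancy outside the serious adverse event (SAE) definition unless it or its outcome meets 9.5. The second sets the duty: "However, pregnancy in subjects that have received the study drug must be followed to assess congenital anomalies". It attaches no causality condition, and names no recipient, deadline or end of follow-up.

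**Reporting.** Protocol 9.5 lists, among events that are serious whatever their cause, one that "is a congenital anomaly/birth defect". Protocol 9.6 gives SAEs during the study an email or fax route and a 24-hour limit from the investigator's awareness. It also sets the window: "Adverse events, both serious and non-serious, will be reported between Day 1 (Enrollment) and the final visit", that is, Week 26 for TEN-01-302 entrants or Week 39 for TEN-01-301 entrants. Protocol 9.7 ends eCRF recording at the same visit. Its later rule, with a 48-hour limit, covers "Any serious adverse event that occurs at any time after completion of the study, which the Investigator considers to be related to study drug".

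**What completion means.** The term is not defined. Protocol 10.7.1 uses it per subject, counting those "who complete the study, and who withdraw early from the study will be presented". Protocol 11.8 uses similar words for close-out: "At the completion of this trial, all unused, partially unused, or empty multiple-dose bottles must be returned to Ardelyx". Protocol 8.2.1.1 adds a third expression: "Adverse events, including serious adverse events will be recorded in the eCRFs through the end of the study".

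**Dosing.** Women of child-bearing potential may enrol with a negative test and contraception (5.2). Pregnancy is an enrolment exclusion (5.3). A positive urine test leads to a serum test (section 7, footnote g; 8.2.1.5). Protocol 5.6 makes discontinuation mandatory only for a drug-related SAE; otherwise the investigator may remove a subject. Protocol 6.3 restricts dispensing to eligible subjects.

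The SAP repeats the pregnancy-test schedule and adds nothing on pregnancy.

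**The concern.** The duty in 9.8 and the reporting rules in 9.6 and 9.7 do not fit together. Follow-up of an exposed pregnancy has no causality condition and will usually outlast the subject's time in the study. The only sponsor-reporting rule written for the later period does have a causality condition. Read literally, one investigator's judgement that an anomaly is unrelated could mean that no one has to tell the sponsor, which is the party placed to compare cases across the planned 50 to 60 sites. With few pregnancies, each one carries weight.

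The dosing gap is separate. A woman with a confirmed pregnancy is not required by any sentence in the protocol to stop tenapanor. Safety is this study's only objective, so both matters bear on its purpose, although neither affects a planned analysis.

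**Working it through.** The plan gives no figure on this point. The check is a reading of the rules side by side, then timing.

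**1. Which rule applies when**

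| Event | Sponsor-reporting rule |
|---|---|
| Pregnancy itself, no 9.5 criterion met | None stated, no deadline |
| Anomaly counted as an SAE during the study | 9.6: any causality, 24 hours |
| Anomaly after completion, judged related | 9.7: 48 hours |
| Anomaly after completion, judged unrelated | None stated |

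The passage in 9.7 on SAE follow-up data presupposes an SAE already reported. The duty to notify all SAEs in 9.6 and 9.7 is owed to the IRB. Section 12 obliges the investigator to supply data obtained during the study and sets no deadline.

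**2. Births against the subject's final visit**

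Inputs from the protocol: final visit at T = 26 ± 2 weeks (TEN-01-302 entrants) or 39 ± 2 weeks (TEN-01-301 entrants). Assumptions, not in the documents: conceptions evenly spread over treatment, and birth g = 35 to 40 weeks after conception.

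Share of births after the final visit = min(1, g/T).

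- TEN-01-302: T is at most 28, below 35, so 100%.
- TEN-01-301: lowest 35/41 = 85.4%; at T = 39, 35/39 = 89.7% and 38/39 = 97.4%; with g = 40 at T = 39, 100%.
- Counting conceptions from 2 weeks before Day 1, the TEN-01-301 minimum is 35/43 = 81.4%.

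These shares suppose that the subject stays to the planned visit. One who leaves early because of pregnancy has her last assessments sooner, so more outcomes would follow them.

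**3. Sensitivity to how an anomaly is dated**

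The same formula at planned T, with g changed (all values of g assumed):

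| Anomaly dated by | g (weeks) | TEN-01-302, T = 26 | TEN-01-301, T = 39 |
|---|---|---|---|
| Birth | 35 to 40 | 100% | 90% to 100% |
| Prenatal scan | 16 to 20 | 62% to 77% | 41% to 51% |
| Occurrence in early gestation | 3 to 10 | 12% to 38% | 8% to 26% |

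**4. Sensitivity to the meaning of completion**

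If completion means trial close-out, let enrolment be uniform over A weeks (A = 13 to 52, assumed; accrual is not given) and close-out fall at A + 39. The share is P(e + c + g > A + 39), with e uniform on (0, A) and c uniform on (0, T), from 2 million simulated draws. For births, g = 35 to 40:

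| A | TEN-01-302 | TEN-01-301 |
|---|---|---|
| 13 | 60% to 79% | 73% to 86% |
| 26 | 36% to 54% | 56% to 69% |
| 52 | 18% to 27% | 30% to 39% |

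For scans (g = 16 to 20) the shares over A = 13 and A = 52 fall to 0% to 7% (TEN-01-302) and 6% to 35% (TEN-01-301).

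**5. Tablets already held**

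Three bottles of 66 make 198 tablets; 198/2 = 99 days at two a day. From each scheduled telephone contact to the next visit: 13 − 5 = 8, 13 − 9 = 4, 26 − 17 = 9, 26 − 22 = 4, 39 − 30 = 9 and 39 − 35 = 4 weeks. A pregnancy disclosed by telephone could thus leave 4 to 9 weeks of planned dosing from tablets at home. A limit on new dispensing does not reach those. This is the most that the schedule allows, not a forecast.

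**The case against.** The case on the other side is substantial.

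- **A route exists for in-study anomalies.** An outcome meeting 9.5 during the study falls under the 24-hour rule. This stands: a reader might infer that anomalies have no reporting route at all, and the text does not support that.
- **Occurrence is not detection.** Both 9.6 and 9.7 turn on when an SAE occurs, and a structural anomaly exists before anyone sees it. This stands. A reader might infer that 85% to 100% of anomalies would escape reporting. Those are shares of births, and dating by occurrence gives far smaller figures. The protocol does not say which date counts.
- **The causality filter is not tight.** Under 9.4, a reasonable temporal sequence can be enough for the possibly-related category, so an anomaly after exposure in the womb will often qualify. This narrows the gap without closing it, since a not-related judgement remains available.
- **Monitors could find the case.** Under 9.6 the IRB notice is to be filed in the regulatory binder, and 11.6 gives monitors access to that binder and to medical records. Pregnancy tests are listed among the central-laboratory tests. These help while a site is open, but they are untimed and do not replace a duty to report.
- **Investigators can already stop drug.** Protocol 5.6 allows removal at once, and pregnancy is tested at each post-enrolment visit. A reader might infer that pregnant subjects would be kept on tenapanor. The documents show only that stopping is not compulsory.
- **Unseen material.** The Study Manual is not in the documents and may hold a pregnancy procedure. The protocol mentions only SAE forms there.

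**Conclusion.** The point holds in a limited form. The protocol requires exposed pregnancies to be followed but not notified to the sponsor. If an anomaly is first seen at birth and judged unrelated, the text can be followed to the letter without the sponsor being told. Under the 35-to-40-week assumption nearly all births from on-study conceptions fall after the subject's final visit. The share of anomalies affected cannot be fixed from the documents: it depends on dating by occurrence or detection, on whether completion is per subject or per trial, on accrual, and on how many anomalies are found prenatally. The number of pregnancies is not given and is probably small, because contraception is required.

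Separately, stopping study drug on a confirmed pregnancy is discretionary, and the dispensing limit does not cover tablets already held.

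This is a cheap improvement for patient safety. It does not challenge the planned analyses.

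**What to change.** In 9.7 and 9.8:

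- require notice of each pregnancy to the sponsor within 24 hours of awareness;
- require follow-up to outcome;
- require any congenital anomaly in an exposed pregnancy to be reported within 24 hours of awareness, regardless of causality or timing.

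The last item makes the dating question and the meaning of completion irrelevant for anomalies. For other late events, 9.7 should still say whether completion means the subject's final visit or trial close-out.

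In 5.6 and footnote g of the schedule: require study drug to be stopped, and no more dispensed, after a confirmed positive test.

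Make both changes together. Stopping drug may bring the last visit forward, and without the reporting change more outcomes would then fall after it.

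The cost is a few sentences, a pregnancy form (unless the Study Manual already has one) and a few follow-up contacts. There are no new visits or subjects, and no planned analysis changes.

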10. STATISTICAL CONSIDERATIONS

This open label long-term safety study will evaluate the safety of tenapanor in subjects with constipation predominant IBS (IBS-C) who have completed either study TEN-01-301 or TEN-01-302. Approximately, 300 subjects who qualify will be enrolled at approximately 50-60 US clinical centers and receive tenapanor 50 mg BID for up to 52 weeks total (previous protocol and this study).

. A statistical analysis plan (SAP) will be developed, finalized, and signed-off on prior to the database lock. This plan will confirm the analysis sets used in the analysis, outline all data handling conventions, and specify all statistical methods to be used for all safety analyses. A set of table, listing, and figure shells will also be part of this plan for internal use. Any changes to the statistical considerations described in Section 10 of this protocol will be addressed in the SAP and will not be part of a protocol amendment.

10.1. Determination of Sample Size

Based on the two Phase 3 studies (TEN-01-301 and TEN-01-302) and the different treatment arms, 300 subjects entered into this open label long-term safety study should produce approximately 150 subjects with at least 52 weeks exposure to tenapanor 50 mg BID and an additional 150 subjects with 26 to 39 weeks of exposure to tenapanor 50 mg BID.

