16.1 Study Information

16.1.1 Protocol and protocol amendments

The following documents are included:

- Final protocol, dated 29 Jan 2016.

CLINICAL STUDY PROTOCOL

Protocol No. TEN-01-303

An Open Label Long-Term Safety Study of Tenapanor for the Treatment of Constipation-Predominant Irritable Bowel Syndrome (IBS-C)

29 January 2016
Edition No. 1

SPONSOR:

Ardelyx, Inc.
[name]
[name]

Confidentiality Statement

This document and the information contained herein or attached hereto ("Confidential Material") are confidential and proprietary to Ardelyx, Inc. This Confidential Material should be viewed only by those individuals or companies that have been given prior authorization to do so by Ardelyx, Inc. ("Authorized Users"). This Confidential Material should not be made available in any form to any person or company, other than the Authorized Users and their respective employees or associates on a need-to-know basis, without the prior written consent from Ardelyx, Inc.

PROTOCOL SUMMARY

Study Title	An Open Label Long-Term Safety Study of Tenapanor for the Treatment of Constipation-Predominant Irritable Bowel Syndrome (IBS-C)
Sponsor	Ardelyx, Inc.
Study Phase	3
Treatment Groups	Single treatment group; approximately 300 subjects total
No. of Sites	Approximately 50-60
Dose Form and Frequency	Tablet(s) Twice daily (BID)
Doses	Tenapanor 50 mg BID (total daily dose 100 mg)
Methodology	This is an open label study to evaluate the safety of tenapanor 50 mg BID in subjects with IBS-C (Rome III criteria). Subjects who have completed either the TEN-01-301 (16 weeks) or TEN-01-302 (26 weeks) studies may be enrolled. Subjects will take tenapanor for up to 52 weeks total based on previous protocol and this study.
Duration	For each subject, the entire exposure to tenapanor will last for a total of approximately 52 to 55 weeks; including completion of either the TEN-01-301 or TEN-01-302 studies. For subjects completing studies TEN-01-301 or TEN-01-302, TEN-01-303 treatment duration will be 39 and 26 weeks, respectively.

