10.7. Statistical Analyses

Summary tabulations will be presented that will display descriptive statistics by visit for four treatment cohorts and for all subjects in the safety analysis set. These cohorts are identified below.

Table 10-1 Treatment Cohorts for Summary Tabulations

	Protocol 301		Protocol 303
Cohort	12-weeks	4-weeks	39-weeks
1	Tenapanor 50 mg BID	Tenapanor 50 mg BID	Tenapanor 50 mg BID
2	Tenapanor 50 mg BID	Placebo	Tenapanor 50 mg BID
3	Placebo	Tenapanor 50 mg BID	Tenapanor 50 mg BID
	Protocol 302		
	26-weeks		26-weeks
4	Tenapanor 50 mg BID		Tenapanor 50 mg BID
5	Placebo		Tenapanor 50 mg BID

The number of observations, mean, standard deviation, minimum, median, and maximum values will be displayed for continuous variables, and the number and percent of subjects per category will be displayed for categorical data.

As this is an open label study of only treatment with tenapanor 50 mg BID, no statistical testing will be done.

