2.2.3 Duration of Study

For each subject, the entire study will last for a total of approximately 52 to 55 weeks; including completion of either the TEN-01-301 or TEN-01-302 studies. For subjects completing studies TEN-01-301 or TEN-01-302, TEN-01-303 treatment duration will be 39 and 26 weeks, respectively. The study flow chart, including all procedures to be performed during the study is presented below.

SCHEDULE OF ASSESSMENTS FOR THE STUDY

The study flow chart, including all procedures to be performed during the study is presented below. Prior to engaging in any study procedure, each subject must sign and date an informed consent form. In addition, a telephone contact will take place as footnoted below to find out if any treatment related problems have occurred. Additional telephone calls to the subjects for treatment follow-ups of AEs will be made as needed.

Evaluation	Enroll ^a	Treatment Period		
		1	2	3 ^b
Site Visit ^h	1	2	3 ^b	4/ET ^c
Study Week	1	13±2	26±2	39±2
Informed Consent ^a	X			
Inclusion/Exclusion	X			
Concurrent Medications		X	X ^{b#}	X
Physical Exam			X ^b	X
Vital Signs ^d		X	X ^{b#}	X
Clinical Laboratory Tests ^f			X ^b	X
Urine Pregnancy test ^{fg}		X	X ^{b#}	X
Urinalysis ^f			X ^b	X
12-lead ECG			X ^b	X
Drug Dispensed/returned	D	D/R	D [#] /R ^{b#}	R
Adverse Event Assessments		X	X ^{b#}	X

^a The Informed Consent Form (ICF) must be signed before any protocol procedures are performed.

^b This is the final visit for subjects who enrolled from Protocol TEN-01-302 and only procedures with this footnote are performed. Procedures for subjects enrolled from Protocol TEN-01-301 are marked with a #.

^c This is the final visit for subjects who enrolled from Protocol TEN-01-301.

^d Vital signs include systolic and diastolic blood pressure (seated), heart rate, respiratory rate, temperature and body weight.

^e When a subject discontinues early, procedures performed at Visit 4 should be performed at the subject's last visit.

^f Laboratory assessments are detailed in Appendix A of the protocol.

^g If the urine pregnancy test is positive, it will be confirmed with a serum pregnancy test.

^h Telephone calls will be made to subjects monthly during the two months prior to a site visit to ascertain if there have been any treatment related problems (Weeks 5±1, 9±1, 17±1, 22±1, for subjects from TEN-01-301 and TEN-01-302 and for subjects from TEN-01-301 also Weeks 30±1 and 35±1).

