3. STATISTICAL METHODOLOGY

3.1 Determination of Sample Size

Based on the two Phase 3 studies (TEN-01-301 and TEN-01-302) and the different treatment arms, 300 subjects entered into this open label long-term safety study should produce approximately 150 subjects with at least 52 weeks exposure to tenapanor 50 mg BID and an additional 150 subjects with 26 to 39 weeks of exposure to tenapanor 50 mg BID.

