3.6.4 Study Drug Exposure and Compliance

Days of exposure to study drug will be summarized with descriptive statistics by treatment cohort and all subjects overall. In addition, a contingency table will be provided to display the number and percentage of subjects in each treatment cohort and overall with exposure in the following categories: ≤ 13 weeks, >13 to ≤ 26 weeks, and >26 weeks.

Days of possible exposure is defined as:

$$\text{date of last dose of study drug} - \text{date of first dose of study drug} + 1.$$

When the last known dose date is missing, the last known clinic visit date during the treatment period will be used, and the plus 1 will be removed from the calculation.

Summary statistics will also be presented for percent compliance to study drug. The percent compliance to study drug will be calculated as the total number of tablets dispensed minus the total number of tablets returned divided by two times the number of days during the treatment period, then multiplied by 100.

Summary statistics will be presented for percent compliance to study drug by treatment cohort and overall. The count and percentage of subjects with overall compliance $<80\%$, $80\%-100\%$, and $>100\%$ will also be tabulated by treatment cohort and overall.

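### The sample-size statement sorts all 300 subjects into two exposure classes that do not fit Cohorts 2 and 3, states no dropout allowance, and cannot be checked from the SAP's exposure table

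*Protocol*

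**What the plan says.** Protocol 10.1 says that 300 entrants should give "approximately 150 subjects with at least 52 weeks exposure to tenapanor 50 mg BID and an additional 150 subjects with 26 to 39 weeks" on the drug. SAP 3.1 repeats the statement ("approximately 150 subjects with at least 52 weeks exposure to tenapanor 50 mg BID"). Neither document gives another reason for the number 300.

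The treatment sequences are set out in Protocol 10.7 ("Table 10-1 Treatment Cohorts for Summary Tabulations") and again in SAP 3.6. Three cohorts come from TEN-01-301 (12 weeks, then 4 weeks, then 39 weeks in this study). Two come from TEN-01-302 (26 weeks, then 26 weeks here). Cohort 2 has placebo in the 4-week period, Cohort 3 in the 12-week period, and Cohort 5 for all 26 parent weeks.

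The Protocol Summary describes total exposure in two ways. Under Methodology: "Subjects will take tenapanor for up to 52 weeks total based on previous protocol and this study". Under Duration: "For each subject, the entire exposure to tenapanor will last for a total of approximately 52 to 55 weeks". SAP 2.2.3 attaches the same range to the study instead of the drug: "For each subject, the entire study will last for a total of approximately 52 to 55 weeks".

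For reporting, SAP 3.6.4 says "a contingency table will be provided to display the number and percentage of subjects in each treatment cohort and overall", with categories of up to 13 weeks, over 13 to 26 weeks, and over 26 weeks. Exposure is defined from first to last dose of study drug.

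**The concern.** The two classes are meant to account for all 300 entrants, but there is a gap between 39 and 52 weeks, and the cohort table places two of the five cohorts in it. The statement gives no cohort sizes, no parent-study allocation ratios and no allowance for withdrawal over 26 to 39 further weeks. The exposure table has no cut at 39 or 52 weeks and no rule for adding parent-study exposure.

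The only objective is safety for up to 52 weeks, so the number of people with a year on drug is the figure that most needs to be clear. As written, a reader cannot tell which cohorts count as a year of exposure or how many such subjects are expected. The planned exposure table will not show afterwards whether the target was met.

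**Working it through.** **The plan's own figure.** 150 + 150 = 300, which is every entrant.

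**Planned tenapanor weeks**, from Protocol Table 10-1 and the matching table in SAP 3.6. The window column moves only the final visit, by the ±2 weeks in the schedule of assessments; parent periods are taken as exact, because the documents do not give the parent visit windows.

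| Cohort | Parent + TEN-01-303 | Total | With window | Class |
|---|---|---|---|---|
| 1 | 12 + 4 + 39 | 55 | 53–57 | at least 52 |
| 2 | 12 + 0 + 39 | 51 | 49–53 | neither |
| 3 | 0 + 4 + 39 | 43 | 41–45 | neither |
| 4 | 26 + 26 | 52 | 50–54 | at least 52, no slack |
| 5 | 0 + 26 | 26 | 24–28 | 26 to 39 |

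On this basis a Cohort 3 completer is outside both classes at every permitted final-visit date. A Cohort 2 completer reaches 52 only if Visit 4 falls at Week 40 or 41.

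**Other counting bases.** On TEN-01-303 exposure alone the totals are 39, 39, 39, 26 and 26, so the 52-week class is empty. On elapsed time they are 16 + 39 = 55 for Cohorts 1 to 3 and 26 + 26 = 52 for Cohorts 4 and 5, so the 26-to-39 class is empty. No single basis fills both classes and covers all five cohorts.

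**A reading that yields 150/150.** Set tenapanor-first subjects (Cohorts 1, 2, 4) against placebo-first subjects (Cohorts 3, 5). With an assumed 1:1 allocation in both parents this is 150 and 150 for any mix of the two studies. It requires counting Cohort 2's 51 weeks as at least 52. It also uses parent plus TEN-01-303 exposure for the first class and TEN-01-303 exposure alone for the second, which leaves out Cohort 3's 4 tenapanor weeks in TEN-01-301.

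**Size, under assumptions.** Let x be the share of entrants from TEN-01-301, p the tenapanor fraction in both parents, and s the share of the TEN-01-301 tenapanor arm kept on tenapanor for the 4-week period. Before dropout:

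- Cohorts 1 + 4 = 300[xps + (1 − x)p]
- Cohort 5 = 300(1 − x)(1 − p)
- Neither class (Cohorts 2 + 3) = 300x(1 − ps)

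| Assumption | x | Cohorts 1 + 4 | Cohort 5 | Neither | Shortfall from 150 |
|---|---|---|---|---|---|
| A: p = s = 0.5 | 0 | 150 | 150 | 0 | 0 |
| A | 0.25 | 131 | 112.5 | 56 | 19 |
| A | 0.5 | 112.5 | 75 | 112.5 | 37.5 |
| A | 0.75 | 94 | 37.5 | 169 | 56 |
| A | 1 | 75 | 0 | 225 | 75 |
| B: p = 2/3, s = 0.5 | 0.5 | 150 | 50 | 100 | 0 |

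The last count but one is zero only if x = 0 (nobody from TEN-01-301) or ps = 1 (no placebo subjects, so Cohort 5 is empty).

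**Dropout.** No rate is given. With an assumed rate d, 150(1 − d) remain: 135, 120 or 105 at 10%, 20% or 30%. To finish with 150 at 52 weeks, 150/(1 − d) rounded up must start in cohorts that can get there: 167, 188 or 215.

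**The SAP exposure table.** Read as TEN-01-303 exposure, a Cohort 1 subject needs 52 − 16 = 36 weeks to total 52, but the top category also takes in 27 to 35 weeks. A Cohort 4 subject who completes exactly 26 weeks, and so 52 in total, falls in the middle category with someone who stopped at Week 14. Read as cumulative exposure, the top category merges 27 to 39, 43, 51 and 52 or more weeks.

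**The Protocol Summary.** A ceiling of 52 weeks conflicts with Cohort 1's 55. A range of 52 to 55 weeks of drug for each subject conflicts with Cohorts 2, 3 and 5 (51, 43 and 26). The same range matches elapsed time, which is how SAP 2.2.3 uses it.

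**The case against.** The strongest reply is that this is loose labelling in a descriptive study. There is no hypothesis test and no power to lose, enrolment is approximate, and no planned summary is biased. On the tenapanor-first versus placebo-first reading, the errors are one week for Cohort 2 and four uncounted weeks for Cohort 3. It is true that power is untouched. But the word for approximation qualifies the number of subjects, not the 52-week threshold, and it cannot bring 43 weeks inside 26 to 39.

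Second, SAP 3.6.1 tabulates completers by cohort, and entry requires completing the parent study, so completers in Cohorts 1 and 4 approximate the 52-week count. The TEN-01-303 categories also suit a study with at most 39 planned weeks. Both points are fair, but the proxy is not exact: a Cohort 4 completer may have 50 weeks. Descriptive statistics of days by cohort do not supply the count either.

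Third, classes that sum to 300 do not prove that zero dropout was assumed. Some early leavers would land in the second class; a Cohort 4 subject who leaves by Week 13 of this study has 26 to 39 weeks in total. That stands, and the narrower statement is that no allowance is given.

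Fourth, no shortfall is demonstrated, because every shortfall figure rests on assumed ratios. That also stands.

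**Conclusion.** The concern holds and should be fixed. On planned cumulative exposure Cohorts 2 and 3 fit neither class, whatever the allocation ratio, and both counts of 150 hold only if no one enters from those cohorts. The visit-window results for Cohorts 2 and 3 additionally assume that parent periods ran exactly to plan.

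The size of any deficit in the 52-week class is unknown: 0 to 75 before dropout under Assumption A, nil under Assumption B. Dropout would lower the 52-week count further. The consequence is for the long-term exposure claim and its reporting, not for any test. The missing 52-week category and the conflict within the Protocol Summary follow directly from the text and need no assumption.

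**What to change.** Protocol 10 allows this to be done in the SAP without a protocol amendment: "Any changes to the statistical considerations described in Section 10 of this protocol will be addressed in the SAP".

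1. **SAP 3.1.** Restate the sentence by cohort: planned cumulative tenapanor weeks (55, 51, 43, 52, 26), the sponsor's expected number per cohort from the actual parent-study ratios, and a stated dropout allowance. Use one basis, parent plus TEN-01-303, for both classes. Either count only Cohorts 1 and 4 as at least 52 weeks, or relabel that class so that it truthfully includes Cohort 2 and say how the 4-week placebo gap counts. Widen the second class so that it covers Cohort 3's 43 weeks.
2. **SAP 3.6.4.** Add a cumulative exposure tabulation with cuts at 39 and 52 weeks, including a category of at least 52 weeks. Define it as days on tenapanor. If the present last-minus-first-dose formula were carried across both studies, it would give Cohort 2 about 12 + 4 + 39 = 55 weeks instead of 51.
3. **Protocol Summary.** Reconcile its two statements of total exposure with Table 10-1 and SAP 2.2.3.

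The cost is rewording, one extra table that uses parent-study dosing dates, and a clarification of the summary. No subjects or visits are added. The drawback is that the stated 52-week figure may become less favourable.
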